6.2. Demographic and Baseline Characteristics

Demographics will be summarized by Module 1a or 1b and dose schedule for the safety population. Baseline demographic will include age at informed consent, age group (<65 and ≥65 years), gender, race, ethnicity, height (cm), weight (kg), BMI (kg/m²). Baseline characteristics will include primary tumor type and ECOG status.

6.3. Genotype and Mutation Status at Enrollment

The genes and mutation status of patients based on local test at enrollment will be listed and summarized.

If a patient tests positive for more than one mutation/gene, the patient will be listed under the mixture of mutation/gene category for the baseline summary.

6.4. Disease Characteristics

The following disease characteristics will be summarized based on the Safety Population:

Disease History:

- Time since initial diagnosis (in years)
- Time since presentation of metastatic disease
- Primary tumor type
- Histology and grade of disease at diagnosis

Prior Anti-Cancer Therapy:

- Number of prior lines of treatment
- Prior irinotecan use
- Prior use of platinum containing regimen
- Information on last prior anticancer therapy:
 - Reason for administration (adjuvant, neoadjuvant, advanced/metastatic, etc.)
 - Best response
 - Disease progression (yes, no)
 - Time since end of last treatment in months
 - Duration of last treatment
 - Reason for end of regimen

6.5. Medical History

Medical history will be coded using the latest version of Medical Dictionary for Regulatory Activities (MedDRA) and will be summarized for the Safety Population, using System OrganClass (SOC) and preferred term (PT). The table will include the number and percentage of subjects and will be sorted in alphabetical order by SOC and PT. A subject will only be counted once within a class. A listing of

medical and surgical history will also be provided. In particular, cancer related medical history will be summarized by SOC and PT.

6.6. Prior and Concomitant Medications

Prior and concomitant medications will be coded using the World Health Organization (WHO) Drug Dictionary. The number and percentage of patients will be tabulated by WHO drug generic term for the Safety Population.

All prior and concomitant procedures (including transfusions) will be recorded from the Screening through to the EOT visit.

Prior medications will include medications which started prior to the date of first dose of study treatment. A summary table will present the numbers and percentages of patients who received prior therapy, including prior systemic anticancer therapy, prior radiation, prior surgery, and best response to the prior therapy, if known. Concomitant medications will include medications which started or were ongoing at the date of first dose of study treatment through to 30 days after the last dose of study treatment, or to the start of subsequent anticancer therapy, whichever occurs first. For Concomitant medications (including transfusions), the generic name of the drug (or trade name for combination drugs) must be specified along with the reason for use, and duration of treatment.

The number of patients with a transfusion, reason for transfusion and type of transfusion will be provided in a listing.

Details of prohibited concomitant medications are provided in the protocol. To determine prohibited medications programmatically, a coded list of all prohibited medications will be provided by clinical team. Listings of prior and concomitant medications will display a flag for prohibited medications. This information will be used to identify protocol deviations.

7. SAFETY AND EXPOSURE DATA

Safety and tolerability will be assessed in terms of AEs, TEAEs, SAEs, DLTs, concomitant medications, PEs, vital sign measurements, clinical safety laboratory evaluations (hematology, serum chemistry, and urinalysis), ECOG performance scores, and ECGs including QTc.

Toxicity will be assessed using the National Cancer Institute (NCI) Common Terminology Criteria for Adverse Events (CTCAE) Version 5.0 unless otherwise specified. A toxicity will be considered dose-limiting if it occurs during the first 28 days, it is deemed to be related to treatment and it meets the criteria defined in Appendix 1. The **DLT Evaluable Population** will be used as the analysis set during dose escalation to make dose decisions in determining the MTD. By-subject listings will be provided for DLTs (Cycle 2) using **DLT Evaluable Population**.

DLTs will be identified from the AE eCRF where the AE is selected as a DLT. All AEs reported as DLTs on the eCRF will be included even if they were not considered DLTs by the Safety Review Committee (SRC) during the study reviews.

The MTD for this study will be defined as the highest dose with the toxicity probability (DLT rate) <25%. The BOIN drug combination design will be employed to find the MTD of continuous RP-6306 (Module 1a) or intermittent RP-6306 (Module 1b) in combination with FOLFIRI. Module 1a and 1b will be evaluated separately based on target toxicity rate is 25%. Simulations confirm that with this study design, defining the MTD this way is equivalent tousing an isotonic regression with a descending pooled

adjacent violators algorithm, which is the recommended method in the publication for BOIN study designs (Yuan et al., 2016).

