If anti-tumor activity is observed at a dose level that is lower than the current dose level being explored (after escalation has proceeded to a higher dose level), additional patients (N≤6), preferably with the same tumor/genomic alteration, may be enrolled at the lower dose level to further confirm safety and efficacy at that dose level. The relevant DLTs from the backfill cohorts will be included in the MTD and RP2D determination by the SRC. Additionally, intrapatient dose escalations for patients at a lower dose level will be allowed at the discretion of the Investigator, and with Sponsor approval and guidance by the SRC, if the higher dose level was deemed safe by the SRC.

Figure B: Module 1a and 1b Escalation Schema Module 1a: RP-6306 + FOLFIRI **MTD** Module 1b: RP-6306 + FOLFIRI Dose Finding (14 Day Cycles) Dose Finding (14 Day Cycles) RP-6306 Continuous QD FOLFIRI Days 1 and 2 RP-6306 3 Days On / 4 Days Off FOLFIRI Days 1 and 2 **MTD** Level R: DLT Safety or intolerability Cohort sizes at each dose level will be guided by BOIN drug combination criteria Cohort sizes at each dose level will be guided by BOIN drug combination criteria

BOIN=Bayesian optimal interval; DLT=dose-limiting toxicity; MTD=maximum tolerated dose;

Table A: **Dose Escalation Tables**

(A1) Dosing Regimens for Module 1a (Continuous RP-6306)^a

Treatment Frequency	Drug	Route of Administration	Dose Level 1 ^b (Starting Dose)	Dose Level 1 ^b and above	Dose Level R	Dose Level R+1°	Dose Level R+N ^c
Once Daily	RP-6306	Oral	40 mg	120 mg, then escalation up to 100%	Same as Current Dose Level	Per BOIN rules up to 20%-50% increase or MTD in MYTHIC	Per BOIN rules up to 20%-50% increase or MTD in MYTHIC
	Irinotecan	IV over 30-90 min	180 mg/m^2	180 mg/m^2	Same as Current Dose Level	Up to 180 mg/m ²	Up to 180 mg/m²
FOLFIRI	Leucovorin	IV over 30-90 min concurrently with irinotecan	400 mg/m ²	400 mg/m ²	Same as Current Dose Level	400 mg/m ²	400 mg/m^2
once every 2 weeks on	Fluorouracil	IV bolus after leucovorin	400 mg/m^2	400 mg/m^2	Same as Current Dose Level	400 mg/m ²	400 mg/m^2
Day 1 ^d				THEN			
	Fluorouracil	IV continuous infusion; start on Day 1 over 46 hours only	2400 mg/m ²	2400 mg/m ²	Same as Current Dose Level	2400 mg/m ²	2400 mg/m ²
1	* If Dose Level 1 is not tolerated						

	II Dose Level I is not tolerated					
Treatment Frequency	Route of Administration	Drug	Dose Level 1D ^c	Dose Level 2D ^c	Dose Level 3D ^c	
Once Daily	Oral	RP-6306	40 mg	40 mg	40 mg	

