For the purpose of overdose control, doses j and higher levels will be eliminated from further consideration if $Pr(pj > 0.25 \mid data) > 0.95$ and at least 3 evaluable patients have been treated at dose level j, where pj is the true DLT rate of dose level j, j = 1, ..., 5. This posterior probability is evaluated based on the beta-binomial model yj | pj ~ binomial(pj) with pj ~ uniform(0, 1), where yj is the number of patients experienced DLT at dose level j. When the lowest dose is eliminated, stop the trial for

safety. When the lowest dose is eliminated, stop the trial for safety. The above dose escalation/de-escalation and elimination rule can be equivalently presented in Table B, which will be used to conduct the trial.

Table B provides information on the different dose decisions based on number of evaluable patients and the number of DLTs reported. Note, more than 6 patients may be exposed at a dose level to better define the MTD.

 Table B:
 Dose Escalation/De-escalation Rules for the BOIN Design

		Number of Evaluable Patients at Current Dose Level										
Action	1	2	3	4	5	6	7	8	9	10	11	12
↑ if number of DLT ≤	0	0	0	0	0	1	1	1	1	1	2	2
Stay current dose if number of DLT =	NA	NA	NA	1	1	NA	2	2	2	2	3	3
\downarrow if number of DLT \geq	1	1	1	2	2	2	3	3	3	3	4	4
Elim if number of DLT ≥	NA	NA	3	3	3	4	4	4	5	5	6	6

BOIN = Bayesian optimal interval; \(\geq = \text{increase}, \quad = \text{decrease}, \text{DLT} = \text{dose-limiting toxicity}, \\ \text{Elim=eliminate}, \text{NA} = \text{not applicable}, \text{dose cannot be eliminated until at least 3 patients have been treated}

Note: Number of DLT is the number of patients with at least 1 DLT. When none of the actions (ie, escalate, de-escalate or eliminate) is triggered, stay at the current dose for treating the next cohort of patients.

Dose finding starts at Dose Level 1. The steps to implement the BOIN design are described as follows:

- 1. Patients in the first cohort are treated at Dose Level 1. Dose decisions will depend on 2 or more evaluable patients completing the first 2 14-day treatment cycles.
- 2. To assign a dose to the next cohort of patients, conduct dose escalation/de-escalation according to the rule displayed in Table B. When using Table B, please note the following:
 - a. "Eliminate" means eliminate the current and higher doses from the trial to prevent treating any future patients at these doses because they are overly toxic.

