 - b. When we eliminate a dose, automatically de-escalate the dose to the next lower level. When the lowest dose is eliminated, stop the trial for safety. In this case, no dose should be selected as the MTD.
 - c. If none of the actions (i.e., escalation, de-escalation or elimination) is triggered, treat the new patients at the current dose.

- d. If the current dose is the lowest dose and the rule indicates dose de-escalation, treat the new patients at the lowest dose unless the number of DLTs reaches the elimination boundary, at which point terminate the trial for safety.
- e. If the current dose is the highest dose and the rule indicates dose escalation, treat the new patients at the highest dose.
- 3. Repeat Step 2 until the maximum sample size of 36 evaluable patients is reached or stop the trial early if the number of evaluable patients treated at the current dose ≥9 and the decision according to Table B is to stay at the current dose.

After the study is completed, results from all DLT evaluable patients, including the relevant backfill cohorts, will be included to assess the MTD. The dose for which the isotonic estimate of the toxicity rate is closest to and no higher than 30% will be selected as the MTD. This computation can be implemented by the shiny app "BOIN" available at http://www.trialdesign.org. The RP2D for RP-6306 and FOLFIRI will be based on discussion between the Investigators and the Sponsor and will be either the established MTD or a dose lower than MTD based on the totality of the safety, PK, pharmacodynamics, and preliminary efficacy.

Dose-Limiting Toxicity Criteria:

Toxicity will be assessed using the National Cancer Institute (NCI) Common Terminology Criteria for Adverse Events (CTCAE) version 5.0 unless otherwise specified. A toxicity will be considered dose-limiting if it occurs during the first 2 cycles (28 days), meets the predefined criteria for DLT, and is deemed at least possibly related to study treatment. If multiple toxicities occur, the most severe toxicity will be used in the assessment.

A DLT is defined as any of the TEAEs (a TEAE is any event that was not present prior to the initiation of study treatment or any event that worsens in either intensity or frequency following exposure to study treatment and for up to 30 days following the last dose of study treatment) listed below that is not clearly and incontrovertibly due to disease progression or extraneous causes.

DLTs will be defined as any of the following:

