APPENDIX 6. SIMULATED OPERATING CHARACTERISTICS OF DOSE ESCALATION DESIGN

Table 22 shows the operating characteristics of the proposed design for this study with 5 scenarios involving various numbers and locations for the MTDs, based on 5000 simulations using the BOIN Design Desktop Program. The computer simulations allow operating characteristics of the design to be estimated, such as the expected proportion of patients who will be either under- or over-dosed, how accurately the true MTD will be identified and how many patients are expected to be exposed to each dose level. The proportion of patients over-dosed, defined as receiving a dose that had a true dose-limiting toxicity rate of >30%, ranged between 15.6% and 28.5% across all assumed dose-toxicity models. The operating characteristics also shows that the design selects one of the true MTD(s), if any, with high probability and allocates more patients to the dose levels with the dose-limiting toxicity rate closest to the target of 0.25.

Table 1: Operating Characteristics of the Drug Combination BOIN design

	Dose Level			Number of	% Early			
	1	2	3	4	5	6	Patients	Stopping
Scenario 2								
True DLT Rate	0.12	0.25	0.42	0.46	0.51	0.55		
Selection %	24.8	62.4	11.1	1.5	0.1	0.0		0.2
% Pts Treated	27.2	47.9	20.3	3.8	0.7	0.1	21.6	
Scenario 3								
True DLT Rate	0.04	0.12	0.25	0.43	0.53	0.63		
Selection %	1.2	30.9	57.2	10.0	0.6	0.0		0.0
% Pts Treated	7.6	36.2	37.8	15.5	2.7	0.3	24.1	
Scenario 4								
True DLT Rate	0.02	0.05	0.08	0.10	0.25	0.40		
Selection %	0.1	3.7	8.3	22.0	52.0	13.9		0.0
% Pts Treated	1.9	15.6	17.5	25.5	27.7	11.7	28.5	
Scenario 5								

True DLT Rate	0.02	0.04	0.06	0.09	0.11	0.25		
Selection %	0.1	2.0	4.4	9.5	24.2	59.9		0.0
% Pts Treated	1.5	14.4	16.5	18.0	25.1	24.5	27.9	

BOIN=Bayesian optimal interval; DLT=dose-limiting toxicity; Pts=patients.

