After the study is completed, results from all DLT evaluable patients, including the relevant backfill cohorts, will be included to assess the MTD. The dose for which the isotonic estimate of the toxicity rate is closest to and no higher than 30% will be selected as the MTD. This computation can be implemented by the shiny app "BOIN" available at http://www.trialdesign.org. The RP2D for RP 6306 and FOLFIRI will be based on discussion between the Investigators and the Sponsor and will be the dose that at or lower than the MTD based on the totality of the safety, PK, pharmacodynamics, and preliminary efficacy.

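### The SAP and protocol give two incompatible rules for selecting the MTD (isotonic estimate up to 30% versus DLT rate below 25%), and the SAP's equivalence claim does not reconcile them

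*SAP*

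**What the plan says.** The target DLT rate is 25% throughout. Three places say how the MTD is chosen at the end:

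- Protocol Synopsis (Maximum Tolerated Dose) and SAP 3.2.2, in the same words: the dose for which "the isotonic estimate of the toxicity rate is closest to and no higher than 30% will be selected as the MTD".
- SAP 7: "The MTD for this study will be defined as the highest dose with the toxicity probability (DLT rate) <25" per cent. It does not say whether this rate is raw or isotonic.

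SAP 7 continues: "Simulations confirm that with this study design, defining the MTD this way is equivalent" to isotonic regression with pooling of adjacent violators. No results are shown for this in the documents supplied.

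Other text that bears on the point:

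- SAP 3.2.2 and the Synopsis count backfill: "results from all DLT evaluable patients, including the relevant backfill cohorts, will be included to assess the MTD". The Synopsis allows it below the current level: "additional patients (N≤6), preferably with the same tumor/genomic alteration, may be enrolled at the lower dose level".
- Dose finding ends at 36 evaluable patients, or earlier if "the number of evaluable patients treated at the current dose ≥9 and the decision according to Table B is to stay" at that dose.
- Cohort size is not fixed: "Dose decisions will depend on 2 or more evaluable patients".
- Protocol Appendix 6 says the design "allocates more patients to the dose levels with the dose-limiting toxicity rate closest to the target of 0.25". It reports one selection percentage per dose and does not compare MTD rules.

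**The concern.** The rules differ in the ceiling (30% or 25%), in the boundary (at most, or strictly below) and possibly in the estimate (isotonic, or unspecified). Two of the three statements are in the SAP itself, so giving the protocol precedence would not make the SAP consistent.

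Defining the MTD is part of a primary objective, and SAP 3.2.2 places the RP2D at or below it. Dose assignment during the trial is not affected, because it follows Table B under either rule. What is affected is the final declaration: the same data can yield two different MTDs, or an MTD under one rule and none under the other. Adjacent levels can be far apart (40 and 120 mg for Levels 1 and 2) or closer (20–50% steps after Level R). With both rules on file, the choice between them could be made after the data are seen.

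**Working it through.** **1. Table B reproduces.** With φ = 0.25, φ₁ = 0.6φ = 0.15 and φ₂ = 1.4φ = 0.35:

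- λₑ = ln(0.85/0.75) / ln[(0.25×0.85)/(0.15×0.75)] = 0.1252/0.6360 = 0.1968 (stated 0.197)
- λ_d = ln(0.75/0.65) / ln[(0.35×0.75)/(0.25×0.65)] = 0.1431/0.4796 = 0.2984 (stated 0.298)

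Eliminating a dose when P(p > 0.25) > 0.95 under a Beta(1+y, 1+n−y) posterior, n ≥ 3, gives the printed elimination row. All 48 cells match.

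**2. Where the rules part.** The eight stay cells are 1/5 and 2/10 (20.0%), 2/9 (22.2%), 1/4, 2/8 and 3/12 (25.0%), 3/11 (27.3%) and 2/7 (28.6%). The last five pass the 30% ceiling and fail the strict 25% one. Of these, 3/11 and 3/12 have n ≥ 9 and so can stop dose finding.

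**3. Two paths that use only Table B decisions** (counts cumulative by level):

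- *Cohorts of 3.* L1 0/3 up; L2 1/3 down; L1 0/6 up; L2 1/6 up; L3 2/3 down; L2 3/9 down; L1 0/9 up; L2 3/12 stay, stop. Isotonic estimates are 0, 25.0% and 66.7%. SAP 3.2.2 gives L2; SAP 7 gives L1.
- *Cohorts of 2 to 4, no tie at 25%.* L1 0/2 up; L2 0/2 up; L3 1/2 down; L2 1/4 stay; L2 1/6 up; L3 1/4 stay; L3 2/7 stay; L3 3/11 stay, stop. Isotonic estimates are 0, 16.7% and 27.3%. SAP 3.2.2 gives L3; SAP 7 gives L2.

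**4. How often.** Assumptions: six ordered levels with the true rates of Appendix 6 Scenarios 2–5, Level 1 start, the written stop rule, maximum 36, no backfill, no SRC discretion. There were 50,000 trials per setting (Monte Carlo SE at most 0.22 points). Closest is read as closest to 30%, and of equal isotonic estimates the higher dose is taken. Percentage of trials in which the rules choose differently:

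| Cohort size (assumed) | Sc. 2 | Sc. 3 | Sc. 4 | Sc. 5 |
|---|---|---|---|---|
| 2 | 30.0 | 27.5 | 25.6 | 23.7 |
| 3 | 25.7 | 20.8 | 12.6 | 12.1 |
| 4 | 53.1 | 46.5 | 37.2 | 35.6 |
| 2, with ≤25% in place of <25% | 12.6 | 11.0 | 9.4 | 8.1 |
| 3, with ≤25% | 10.4 | 6.7 | 1.7 | 1.9 |
| 4, with ≤25% | 3.0 | 1.2 | 0.0 | 0.0 |

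In every disagreement SAP 7 gave the lower dose or no MTD. It gave none where SAP 3.2.2 gave one in 7.4/7.5/13.4% of Scenario 2 trials (cohorts of 2/3/4), and in at most 0.8% elsewhere.

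**5. Which rule produced Appendix 6?** Assumed cohorts of 3 from Level 2, stopping when n ≥ 9 and the dose is unchanged. Level 2 is inferred because Scenario 5 puts only 1.5% of 27.9 = 0.4 patients at Level 1. Mean sample size from 5,000 trials per scenario is 21.4/24.0/28.5/28.0 against the stated 21.6/24.1/28.5/27.9. Selection (%) of the dose with true rate 0.25:

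| Rule | Sc. 2 | Sc. 3 | Sc. 4 | Sc. 5 |
|---|---|---|---|---|
| Stated in Appendix 6 | 62.4 | 57.2 | 52.0 | 59.9 |
| Isotonic, closest to 25%, no cap | 61.4 | 56.3 | 52.2 | 60.0 |
| Isotonic, closest to and ≤30% | 57.7 | 53.9 | 47.2 | 48.4 |
| Highest dose <25% | 44.7 | 41.3 | 38.2 | 43.2 |

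Only a third rule, not written as the MTD rule in either document, matches. In this setting the two written rules disagree in 19.8/22.3/16.5/11.5% of trials.

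**6. The equivalence sentence.** Without backfill, raw and isotonic rates with the same <25% cut never gave different doses. With backfill (6 patients at one lower level, or up to 24 over four) they differed in 0.03–1.3% of trials, while the two written rules differed in 12.3–45.9%. Example: L1 0/3, L2 4/9 (six of them backfill), L3 2/9, L4 3/6. L2 and L3 pool to (4+2)/(9+9) = 33.3%. SAP 3.2.2 then gives L1, whereas the highest raw rate below 25% is at L3 (22.2%).

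**The case against.** - *The equivalence sentence may claim less.* Its natural reading is the same 25% cut with or without isotonic smoothing, and without backfill that is what the simulations show. The supporting runs may also sit in protocol sections not supplied. This stands, and it is why I call the sentence unsupported rather than false. On that reading, though, it says nothing about the 30% rule.
- *Much of the disagreement is a tie.* Three of the five disputed cells are exactly 25.0%, and with cohorts of 4 nearly all the disagreement is of this kind. This stands. Reading the rule as ≤25% still leaves 8.1–12.6% with cohorts of 2, and how a tie is treated is itself unstated.
- *The model is not this trial.* Cohort size is assumed, and no passage specifies 4. The real design can move either drug, insert intermediate doses and defer to the SRC. This stands, so the percentages are illustrative. The conflict in the text does not depend on them.
- *The backfill reversal is contrived.* It needs DLTs in 4 of 6 backfill patients, and SAP 7 with a raw rate gave the higher dose in at most 0.15% of trials. This stands.
- *Appendix 6's 0.25 is a true rate, whereas SAP 7 would act on an estimate.* This is fair: the <25% rule still picks those doses in 38.2–44.7% of trials. Read literally as a definition, however, a toxicity probability below 25% excludes the most-selected dose in every printed scenario.
- *The first rule is itself ambiguous.* It could mean closest to 30%, or closest to the target with a cap at 30%. This stands. In comparison runs it moved the cohorts-of-2 figures by about 1–2 points and the others by about 0.
- *The stakes are modest.* Assignment is unaffected, SAP 7 is almost always the more cautious rule, and the RP2D may be set below the MTD anyway. This is true, but the MTD is still a primary-objective result that should be determined by the data and a single rule.

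**Conclusion.** The concern holds. The Protocol Synopsis and SAP 3.2.2 conflict with SAP 7, no text supplied resolves the conflict, and the plan's own stop rule can end dose finding at counts where the sections name different MTDs. That follows from the text and Table B alone.

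How often it would matter rests on the assumptions in the working: roughly one trial in eight to three in ten with cohorts of 2 or 3, about a third to a half with cohorts of 4, and 11.5–22.3% in the setting that best matches Appendix 6. The equivalence sentence does not remove the conflict, and neither written rule reproduces the Appendix 6 selection percentages. This should be settled before database lock, the point by which SAP 1 says the analyses are to be fixed.

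**What to change.** Reconcile the Protocol Synopsis, SAP 3.2.2 and SAP 7 to one pre-specified selection rule, stated identically. It should say:

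- whether the rate is raw or isotonic, with relevant backfill patients counted;
- what the estimate must be closest to, if that wording is kept, and how equal estimates are resolved;
- how an estimate of exactly 25% is handled;
- what is declared if no dose qualifies.

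Substantiate the equivalence sentence in SAP 7, with its conditions, or delete it. Confirm that Appendix 6 was produced under the adopted rule, stating the cohort size, start level and stop rule used; rerun it if not. The choice of toxicity ceiling belongs to the sponsor.

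The cost is wording in one protocol passage (and any matching protocol text not supplied) and two SAP passages, and at most one rerun of the Appendix 6 simulations. No patients and no new data are needed.
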